8.2 Analyses of Secondary Endpoints

8.2.1 PFS

Progression Free Survival (PFS) is defined as the time from the study treatment first dose to the earlier of disease progression or death due to any cause. Disease progression will be assessed using RECIST 1.1. The progression and censoring dates will be based on the May 2007 FDA Guidance for Industry, ‘*Clinical Trial Endpoints for the Approval of Cancer Drugs and Biologics*’. Determination rules for events or censored PFS is summarized in Table 2.

Table 2: Date of Event or Censoring for the Primary PFS analysis

Situation	Date of Event or Censoring	Outcome
Disease progression between scheduled disease assessments	Date of progression	Event
Death between scheduled disease assessment	Date of death	Event
Death before the first planned disease assessment at 6 weeks (plus 1 week window) without any disease assessment	Date of death	Event
No baseline disease assessments	Date of first dose	Censored
No post-baseline disease assessments without death before the first planned disease assessment	Date of first dose	Censored
Discontinuation of study treatment without progression (i.e., due to toxicity, withdrew consent, or lost to follow-up) and no further radiographic assessment ^a	Date of last radiological assessment	Censored
Alternate anticancer treatment started without documentation of disease progression beforehand ^b	Date of last radiological assessment prior to start of further anticancer treatment	Censored
Death or disease progression after missing two or more consecutively scheduled disease assessments ^c	Date of last radiological assessment without documented progression disease prior to death/progression	Censored
Patients who have not progressed and are alive	Date of last radiological assessment without documented progression disease	Censored

- For a patient who discontinues study treatment without PD and continues to have radiographic assessments, post-treatment radiographic assessments will be considered for PFS analyses according to the rules in this table.
- Alternate anticancer treatment interventions that are diagnostic (e.g. biopsy) or palliative (e.g., local radiation for painful nodule), as determined by medical review, will not routinely require censoring unless they are determined to interfere with the assessment of the patients’ disease status.
- Disease assessments are planned every 6 (± 1) weeks for the first 6 months (24 weeks); and every 9 (± 2) weeks, thereafter, until disease progression. The interval of two missed scheduled assessments is calculated according to the

Situation	Date of Event or Censoring	Outcome
scheduled assessment frequency and the corresponding window (1 or 2 weeks depending on assessments scheduled before or after 6 months).		

PFS will be summarized descriptively using the Kaplan-Meier method. Median PFS and its corresponding 95% confidence interval will be reported. Greenwood's formula will be used to calculate the standard errors of the Kaplan-Meier estimate and upper and lower limits of the 95% confidence interval.

The PFS rate and its corresponding 95% confidence interval for various landmark time points (i.e., 6 months and 1 year) will also be estimated using the Kaplan-Meier method. The Kaplan-Meier curve of PFS will be provided.

Subgroup analyses for PFS will be performed, Kaplan-Meier curves and a forest plot will be presented.

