2.2.2 Secondary endpoint(s)

Efficacy

- Duration of response (DOR), defined as the time from response criteria are first met for either complete response (CR) or partial response (PR), until the first date that

progressive disease (PD) is objectively documented, or until death (if death occurs within 9 weeks of the last evaluable scan), for subjects who achieve confirmed CR or PR.

- Progression-free survival (PFS), defined as the time from first dose of study treatment date to first documentation of objective progression or death due to any cause, whichever occurs first.
- Overall survival (OS), defined as the time from first dose of study treatment to death due to any cause.

Safety Endpoints

- Incidence of adverse events
- Deaths on study
- Discontinuations of study drug due to adverse events
- Changes in vital sign parameters
- Changes in hematology, chemistry, and other laboratory parameters
- ECG parameters
- ECOG performance status

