4.2 Response Evaluable Population

Response evaluable population includes subjects who have measurable disease at baseline and receive study treatment, and excludes subjects who discontinue study prior to the first disease assessment without symptomatic deterioration or death. Specifically, patients who discontinue study prior to the first disease assessment for reasons unrelated to study treatment (i.e., adverse events deemed unrelated to study treatment, withdrawal of consent, lost to follow-up, withdrawal due to administrative reasons, etc.) will be excluded from the response-evaluable population and may be replaced. Patients who discontinue study prior to the first disease assessment due to treatment-related adverse events, symptomatic deterioration (adverse events due to progression), or death will be included in the response evaluable population. The primary ORR analysis is based on evaluable population and the secondary analysis will be based on safety (treated) population.

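### On its plain reading, SAP Table 2 censors at first dose a never-scanned patient who dies after missing only one scheduled scan, at odds with the PFS definition and the two-missed-scan row

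*SAP*

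**What the plan says.** SAP section 2.2.2 defines PFS as time from first dose to "first documentation of objective progression or death due to any cause, whichever occurs first". Five rows of Table 2 in SAP section 8.2.1 bear on a patient who dies without a scan after baseline:

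- "Death before the first planned disease assessment at 6 weeks (plus 1 week window) without any disease assessment": event at date of death.
- "No post-baseline disease assessments without death before the first planned disease assessment": censored at first dose.
- "Death between scheduled disease assessment": event at date of death.
- "Death or disease progression after missing two or more consecutively scheduled disease assessments": censored at the last progression-free scan.
- "Alternate anticancer treatment started without documentation of disease progression beforehand": censored at the last scan before that treatment.

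A sixth row censors patients who stop study treatment without progression (its examples are toxicity, withdrawn consent and loss to follow-up) and have no later imaging. It mentions neither death nor a number of missed scans. The table states no order of precedence among its rows.

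Protocol section 11.5.1 has essentially the same rule. A patient lacking baseline or follow-up assessments is censored unless death came before the first planned assessment, and meeting any one listed condition is enough to censor. The protocol does not add the one-week window that the SAP adds.

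**The concern.** Consider a patient with a baseline scan only, who starts no other anticancer therapy and dies at week 9. The first-scan window closed at week 7, so the row for early unscanned deaths no longer applies. The no-post-baseline row then removes the patient at first dose, with no follow-up and no event, although the date of death is known and OS counts it.

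The missed-scan row tolerates one miss. A patient with a week 6 scan who misses week 12 and then dies is an event, unless the alternate-therapy row or, read literally, the treatment-discontinuation row applies. The never-scanned patient with the same single miss is dropped. The plan gives no reason for the difference.

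The censoring is also likely to be informative. Protocol section 7.2.4.1 does not accept symptomatic deterioration as objective progression. A patient who deteriorates before week 6 and is never scanned can therefore have only death as a PFS event. For ORR, SAP section 4.2 provides that patients who leave before the first assessment because of "symptomatic deterioration (adverse events due to progression), or death will be included in the response evaluable population", and SAP section 8.1 counts a missing response as non-response. Where section 4.2 keeps such a patient, he or she is a failure for ORR and contributes nothing to PFS.

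At stake is the later part of the Kaplan-Meier curve, including the two named landmarks of 6 months and 1 year, and what is derived from the same data: PFS subgroups and the gpNMB models.

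**Working it through.** **Which deaths are affected.** Scans fall at weeks 6, 12, 18 and 24, each with a one-week window. The first window closes at week 7 (7 x 7 = day 49). Footnote c takes the two-missed interval from the "scheduled assessment frequency and the corresponding window (1 or 2 weeks depending on assessments scheduled before or after 6 months"). This can be read as 12 + 1 = 13 weeks (day 91) or as 2 x 7 = 14 weeks (day 98). On the day 91 reading, for a patient with no scan after baseline and no other therapy:

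| Week of death | Windows closed | No-scan rows | Two-missed row alone |
|---|---|---|---|
| 5, 6.5 | 0 | event | event |
| 7.5, 9, 10.9, 12.5 | 1 | censored at first dose | event |
| 13.5 | 2 | censored at first dose | censored |

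The conflict is confined to deaths on days 50 to 91 (or 98). Later unscanned deaths are censored either way.

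**The plan's own PFS figure.** The only PFS-based design figure is 36 events for about 80% power in the Cohort 1 gpNMB Cox model (hazard ratio 0.99 per 1%, SD 35, one-sided 10%). It reproduces: (1.2816 + 0.8416)^2 / (35^2 x ln(0.99)^2) = 36.4 events, and power at 36 events is 79.6%. If 1, 2 or 3 of the 36 events were lost through this rule, power would be 78.8%, 77.9% or 77.0%.

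**Effect on the Kaplan-Meier curve.** Let k of n patients be affected, and let S be the curve of the other n-k. A patient censored at first dose is never at risk at an event time, so the reported curve is S throughout. With the k deaths as events and nobody else censored before them, the curve is k/n + (1-k/n)S before week 7 and (1-k/n)S after the last of these deaths. Reported PFS is therefore slightly low before week 7. After about week 13 it is too high by n/(n-k). The documents do not give k; 1 to 3 is assumed, as is a 6-month PFS of 25%.

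| n | k | n/(n-k) | 25% is reported as |
|---|---|---|---|
| 60 | 1 | 1.017 | 25.4% |
| 60 | 2 | 1.034 | 25.9% |
| 60 | 3 | 1.053 | 26.3% |
| 30 | 1 | 1.034 | 25.9% |
| 30 | 2 | 1.071 | 26.8% |
| 30 | 3 | 1.111 | 27.8% |

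For comparison, the approximate 95% half-width 1.96 x sqrt(0.25 x 0.75/n) is 11.0 points for n = 60 and 15.5 points for n = 30.

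**With other early censoring.** Suppose d patients progress and then c others are censored at week 6, leaving R = n-k-d-c others at risk. The ratio is [(n-k-d)/(n-k)] / [((n-d)/n) x R/(R+k)], which simplifies to n/(n-k) x [1 + ck/((n-d)R)]. It cannot fall below n/(n-k). For k = 3:

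- n = 60, d = 15: c = 6 gives (42/57)/(0.75 x 36/39) = 1.064; c = 12 gives 1.081.
- n = 30, d = 8: c = 3 gives 1.140; c = 6 gives 1.181.

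**Worked example (assumed data).** Take n = 60, unscanned deaths on days 63, 70 and 80, progression at weeks 6, 12, 18 and 24 in 17, 12, 8 and 6 patients, and no other censoring.

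| Time | Deaths as events | Censored at first dose |
|---|---|---|
| Week 7 | 43/60 = 71.7% | 40/57 = 70.2% |
| Week 13 | 28/60 = 46.7% | 28/57 = 49.1% |
| 6 months | 14/60 = 23.3% | 14/57 = 24.6% |
| Median | 12 weeks | 12 weeks |

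**The case against.** The strongest reply is that this is a shared convention. Protocol and SAP agree in substance, both cite the same regulatory guidance, and a specific row may properly qualify a general definition. Agreement between the documents does not explain why one missed scan is tolerated with an earlier scan and not without one, so the inconsistency stands.

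Several limits do hold:

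- A reader might infer that Table 2 settles the outcome as censoring. It does not, because the row for deaths between assessments could literally cover a week 9 death. The specific row and the protocol make censoring the plainer reading.
- A reader might infer that every other death is censored only after two misses. The alternate-therapy row also censors, and so, literally, does the treatment-discontinuation row.
- A reader might infer that ORR always counts this patient as a failure. SAP section 4.2 excludes patients who leave before the first assessment for unrelated reasons such as withdrawal or loss to follow-up.
- The day 49 boundary belongs to the SAP only.
- k is probably small. Eligibility requires a life expectancy of at least 12 weeks and ECOG 0 or 1, and Protocol section 7.2.4.1 asks sites to keep scanning after symptomatic deterioration. Three of 30 would be 10% of a cohort.
- The study is open-label, and the protocol already describes Cohorts 1 and 2 as enrolled. A late change to a prespecified censoring rule invites criticism as post hoc. This is a reason to document the timing and to report both versions.

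**Conclusion.** The point holds as an inconsistency of small effect. On the plain reading, an observed death after a single missed scan is removed from PFS if the patient was never scanned after baseline. Another row points the other way, and nothing says which prevails. Where the death is censored, late Kaplan-Meier PFS is biased upward by at least n/(n-k). On the assumptions of k = 1 to 3, a 6-month PFS of 25% and no other censoring before these deaths, that is 0.4 to 2.8 points against half-widths of about 11 to 15.5.

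A reader might infer that the trial's efficacy conclusion or its median PFS is distorted. The documents do not support that: PFS is secondary and summarized descriptively, and the median did not move in the worked example. ORR and OS are unaffected by the no-scan rule, and so is DOR, because responders have scans.

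**What to change.** In SAP Table 2:

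1. Restrict the no-post-baseline row to patients who are alive, or whose death follows two or more consecutive missed assessments.
2. Count an unscanned death after at most one missed assessment as an event at the date of death, unless alternate anticancer therapy (as qualified by footnote b) started first.
3. State that this death rule takes precedence over the treatment-discontinuation row, and apply the same precedence to patients with an earlier scan. The discontinuation row then covers only patients with no death before two missed assessments.
4. Give the two-missed cutoff as a day number (day 91 would parallel the 6 + 1 week rule for the first scan), and date any censored patient without a post-baseline scan at first dose.

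Record the change, and its timing relative to data review, in SAP section 12, which now lists only a population naming change. Report PFS under the protocol's present rule as a sensitivity analysis. Protocol section 11 lets the SAP modify the plan and asks for an amendment only for major changes to the primary endpoint or its analysis, so section 11.5.1 can be aligned at the next revision.

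The cost is one table, one section 12 entry and one extra analysis, with no new data. SAP and protocol would differ for a time, the change comes late in an open-label study, and reported late PFS may be slightly lower. Because SAP section 8.2.2 borrows the PFS censoring rules for DOR, item 3 could also turn a few censored responders into events there; the section 12 entry should say so.

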8.2.2 Duration of response (DOR) and disease control rate (DCR)

Duration of Response (DOR) will be calculated for subjects who achieve confirmed CR or PR. For such subjects, DOR is defined as the time from response criteria are first met for either CR or PR, until the first date PD is objectively documented, or until death. DOR will be right-censored based on the same rules as described for PFS above.

DOR will be summarized descriptively and the median DOR will be estimated using the Kaplan-Meier method.

Swimmer plots will be provided depicting graphically the duration of response for patients who achieve complete response or partial response per RECIST 1.1 in each cohort. For Cohorts 2 and 3, swimmer plots of tumor response will also be provided per irRECIST criteria.

Disease control rate (DCR) is defined as the proportion of evaluable subjects who achieved BOR of CR or PR with any duration or SD with duration of at least 3 months (i.e., ≥ 3 months). The estimate of the DCR will be accompanied by one-sided and two-sided 95% Clopper-Pearson confidence intervals. Additionally, DOR and DCR will be derived and summarized based on the irRECIST criteria for Cohorts 2 and 3 subjects.

8.2.3 Overall Survival (OS)

Overall survival (OS) is defined as the time from first dose to death due to any cause. Subjects who are alive or lost to follow-up as of the data analysis cutoff date will be censored at the last known alive date.

The OS will be summarized descriptively using the Kaplan-Meier method; median OS and its corresponding 95% confidence interval will be reported. Median follow-up for OS will be estimated according to the Kaplan-Meier estimate of potential follow-up (Schemper and Smith 1996). Kaplan-Meier curve of OS will be provided.

8.3 Exploratory Analysis

GpNMB expression will be summarized over time and/or by specific prior therapies.

If feasible, based on the range of gpNMB expression, the correlation between gpNMB expression level and maximum percent decrease from baseline in the sum of longest diameters of target lesions will be evaluated using linear regression. Transformation might be necessary if

data distribution is not normal. For this analysis, all subjects will be used, with gpNMB expression measured on a continuous scale (percentage of gpNMB-positive tumor cells). To examine the predictive power of various cut-off values for gpNMB expression, a receiver operating curve (ROC) analysis for response data ([Gönen and SAS Institute. 2007](#)) will be performed.

The correlation between gpNMB expression levels and efficacy endpoints including ORR, PFS, and OS will be explored using subgroup analyses by gpNMB level categories. Descriptive statistical tests may be used to compare the efficacy endpoint in subjects with different gpNMB level categories, if appropriate. Cox proportional hazard model may also be used to assess the gpNMB effects on PFS and OS by considering gpNMB expression in a continuous and/or categorical scale.

For the above analyses, the most recent tumor sample will be utilized to determine the tumor gpNMB expression level for each patient. Additional exploratory analyses may be performed to examine the distribution and intensity of gpNMB expression (i.e., staining intensity and percentage of positive tumor and stromal cells) relative to outcome, as well as comparison of Historic and Pre-Study samples to determine whether gpNMB expression changes over time and/or with specific prior therapies.

ORR, PFS and OS will be summarized by whether patients experienced rash in cycle 1 which is defined in Section [5.3](#). A by-subject listing will be provided for gpNMB expression data and related efficacy endpoints.

Gene signature from skinfold biopsy samples for cohorts 2 and 3 patients will be analyzed for its correlations with rash in cycle 1 and with ORR and PFS.

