Waterfall plots will be used to depict graphically the maximum decrease from baseline in the sum of longest diameters of target lesions. Correlation between the degree of gpNMB expression and maximum decrease from baseline in the sum of longest diameters of target lesions will be evaluated. For this analysis, all patients will be used, with gpNMB expression measured on a continuous scale (percentage of gpNMB-positive tumor cells). Further, to explore the predictive power of various cut-off values for gpNMB expression, a receiver operating curve (ROC) analysis for the response data ([Gönen and SAS Institute. 2007](#)) will be performed.

The duration of objective response, PFS, and OS will be summarized descriptively for all patients, using the Kaplan-Meier method. The association between the degree of gpNMB expression and PFS will be evaluated using a Cox proportional hazards model. For this analysis, all patients will be used, with gpNMB expression measured on a continuous scale (percentage of gpNMB-positive tumor cells). When a factor is continuous, the hazard ratio is interpreted as the change in risk for each 1-unit increase in the factor. For example, a hazard ratio of 0.99 indicates the hazard for the event decreases by 1% for each 1%-unit increase in gpNMB expression level. For Cohort 1, if a true hazard ratio of 0.99 is assumed and the standard deviation for gpNMB expression level is $\pm 35\%$, 36 PFS events from among the 52 evaluable patients (70% event rate)

	
will provide approximately 80% power with one-sided significance level of 10% (Hsieh and Lavori 2000). The predictive power of various cut-off values for gpNMB expression will be explored based on a receiver operating curve (ROC) analysis for censored data (Gönen and SAS Institute. 2007). Similar analyses will be performed for Cohorts 2, 3, and 5 separately.
 
For the above analyses, the most recent tumor sample will be utilized to determine the tumor gpNMB expression level for each patient. Additional exploratory analyses may be performed to examine the distribution and intensity of gpNMB expression (i.e., staining intensity and percentage of positive tumor and stromal cells) relative to outcome, as well as comparison of Historic and Pre-Study samples to determine whether gpNMB expression changes over time and/or with specific prior therapies.

--	--

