If feasible based on the range of gpNMB expression levels, the association between gpNMB expression level and PFS will be evaluated using a Cox proportional hazards model. For this analysis, patients with gpNMB expression measured on a continuous scale (percentage of gpNMB-positive tumor cells) will be analyzed. When a factor is continuous, the hazard ratio is interpreted as the change in risk for each 1-unit increase in the factor. For example, a hazard ratio of 0.99 indicates the hazard for the event decreases by 1% for each 1%-unit increase in gpNMB expression level. For Cohort 1, if a true hazard ratio of 0.99 is assumed and the standard deviation for gpNMB expression level is $\pm 35\%$, 36 PFS events from among the 52 evaluable patients (70% event rate) will provide approximately 80% power with one-sided significance level of 10% ([Hsieh and Lavori 2000](#)). The predictive power of various cut-off values for gpNMB expression will be explored based on a receiver operating curve (ROC) analysis for censored data ([Gönen and SAS Institute. 2007](#)). Similar analyses will be performed for Cohorts 2 and 3 separately.

Overall Survival

OS is defined as the number of months elapsed between the start date of protocol treatment and the date of death (whatever the cause). OS will be based on the ITT population. Patients who are alive or lost to follow-up as of the data analysis cutoff date will be right-censored. The censoring date will be determined from the patients' date of last contact or data analysis cutoff date, whichever event occurs first. The duration of OS will be summarized descriptively using the Kaplan-Meier method. Median OS and its corresponding 95% confidence interval will be reported. Median follow-up for OS will be estimated according to the reverse Kaplan-Meier estimate of potential follow-up ([Schemper and Smith 1996](#)).

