5.3 Subgroups

Subgroup analyses will be performed to explore the correlation between degree of gpNMB expression and anti-cancer activity of glembatumumab vedotin in advanced melanoma for efficacy endpoints. Rash developed in treatment cycle 1 will also be explored as another subgroup variable. Specifically, the following subgroup analyses will be performed for ORR, PFS and OS:

- Age group (<65, >=65)
- Gender (Female, Male)
- CNS involvement (Yes, No)
- Number of disease site (<=3, >3)
- ECOG PS (0, 1)
- GpNMB Expression (<95%, >=95%)
- Rash in cycle 1 (Yes, No). The medical term of rash is to be defined by medical manual review and documented prior to analysis. Only treatment-related rash is considered. If a subject only has 1 cycle of treatment, rash onset within 21 days from the first dose will be considered as rash in cycle 1.
- Time between last prior CPI and initiation of study treatment (<=3 months, >3 months).
- Duration of last prior CPI (<=3 months, >3 months).

- Cohort 3 only: PD-L1, positive (positive in $\geq 1\%$ tumor cells) vs negative

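### The SAP makes optional the continuous-scale gpNMB Cox model for PFS that the protocol plans and powers, leaves its scale open, and does not list the change

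*SAP*

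**What the plan says.** Whether activity depends on gpNMB expression is a secondary objective in both documents (Protocol Section 6; SAP Section 2.1.2).

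The protocol synopsis is unconditional: "The association between the degree of gpNMB expression and PFS will be evaluated using a Cox proportional hazards model". Section 11.5.1 adds a condition: "If feasible based on the range of gpNMB expression levels, the association between gpNMB expression level and PFS will be evaluated". On the scale, Section 11.5.1 says that "patients with gpNMB expression measured on a continuous scale (percentage of gpNMB-positive tumor cells) will be analyzed". Both places give the same power statement for Cohort 1: a hazard ratio of 0.99 per percentage point, SD 35 points, 36 PFS events among 52 evaluable patients, about 80% power, one-sided 10%. Similar analyses are planned for the other cohorts separately.

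SAP Section 8.3 says that a "Cox proportional hazard model may also be used to assess the gpNMB effects on PFS and OS" and lets gpNMB enter as continuous, categorical or both. For ORR, PFS and OS, the relation to gpNMB "will be explored using subgroup analyses by gpNMB level categories". Section 5.3 commits to subgroup analyses of those endpoints and fixes the gpNMB split at below 95% versus 95% or more. Tests between gpNMB categories are also optional in Section 8.3. Section 12, the list of changes from the planned analyses, records only that the term ITT population is retired.

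**The concern.** The only power statement for the gpNMB objective belongs to a model that the SAP does not require. Neither the model nor a test between categories is mandatory, so the SAP contains no firm inferential analysis of gpNMB and PFS. The scale is open as well. In an open-label study with investigator-assessed progression, the choice between a continuous and a categorical covariate could be made after the results are known. If conclusions then rested on the 95% split, information on expression within each side of the cut would be lost. A reader who compares the SAP with the protocol through Section 12 would not learn of the change.

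**Working it through.** **Inputs (Protocol Section 11.5.1 and synopsis).** Hazard ratio 0.99 per point, so |ln 0.99| = 0.01005; SD 35; D = 36 events; one-sided 10%, so z = 1.2816. The cut at 95% is from SAP Section 5.3.

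**Reproducing the plan's figure.** For a continuous Cox covariate (the Hsieh-Lavori formula):

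- Power = Φ(√D × SD × |ln HR| − z) = Φ(6 × 35 × 0.01005 − 1.2816) = Φ(0.829) = 79.6%.
- Events for 80% power = (1.2816 + 0.8416)² / (35 × 0.01005)² = 4.508 / 0.1237 = 36.4.

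Both agree with the protocol.

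**If a test were made at the 95% split.** Replacing the continuous value by an indicator multiplies the information by r², the squared correlation between the two:

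- Power = Φ(√(36 r²) × 0.3518 − 1.2816).
- Events for 80% power = 36.4 / r².

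r² depends on the distribution of gpNMB, which the documents do not give. The table assumes beta distributions on 0–100% with SD 35. The last column simulates the score test (52 patients, 36 events, 4,000 runs).

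| Assumed mean | Share ≥95% | r² | Power by formula | Events for 80% | Simulated power |
|---|---|---|---|---|---|
| 30 | 8% | 0.32 | 46% | 115 | 35% |
| 40 | 9% | 0.27 | 43% | 134 | 33% |
| 50 | 14% | 0.30 | 45% | 121 | 39% |
| 60 | 24% | 0.38 | 51% | 96 | 44% |
| 70 | 42% | 0.49 | 58% | 74 | 55% |
| 80 | 68% | 0.68 | 67.5% | 54 | 67% |

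In the same simulations the continuous model had 75% to 83% power. The formula therefore flatters the split somewhat when few patients lie at or above 95%.

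**Limiting case.** Suppose every patient is either near 100% or at one low value, with share q near 100%. An SD of 35 then fixes the gap at 35/√(q(1−q)), which is 70 points at q = 0.5. Power is Φ(√(36 × 0.25) × 70 × 0.01005 − 1.2816) = 79.6%, so nothing is lost.

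**Dependence on the SD.** The 80% itself needs an SD of 35. With 36 events, the continuous model has 70% power at SD 30 and 47% at SD 20.

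**The case against.** Several objections have force.

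- Section 11.5.1 of the protocol was already conditional; only the synopsis is not. But the condition concerns the range of expression, which differs from a free option. The SAP itself keeps a feasibility condition with a firm commitment for the regression of tumor shrinkage on gpNMB, and uses the weaker wording only for the Cox model.
- Protocol Section 11 allows the SAP to modify plans and asks for an amendment only for major changes to the primary endpoint or its analysis. The change is therefore permitted. What is missing is its entry in Section 12.
- The SAP calls the study exploratory, with no multiplicity adjustment (Section 5.2), and keeps continuous gpNMB for tumor shrinkage and a ROC analysis for response. This is true, but none of it addresses PFS.

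A reader might go further in four ways that the documents do not support.

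- That the SAP throws away the stated power. The continuous model remains available, and if it is fitted nothing is lost.
- That the SAP replaces it with a test at 95%. The firm element is a subgroup summary, with Kaplan-Meier curves and a forest plot for PFS (SAP Section 8.2.1); tests are optional.
- That the 95% cut is chosen after the results are seen or has no basis. It is fixed in Section 5.3. The SAP gives no rationale, but the protocol's background section is blacked out, so one cannot be ruled out.
- That a uniform spread of gpNMB gives the worst case. A uniform variable on 0–100 has SD 100/√12 = 28.9, which contradicts the protocol's 35. With that SD the continuous model itself would have only about 68% power.

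**Conclusion.** The point holds as a specification gap for a secondary objective. The powered model has moved from planned (if feasible) to optional, its scale is open, and Section 12 is silent. The stated power is at risk, not discarded. The exposure, if inference relied on the 95% split, is a fall from 79.6% to about 43% to 68% under the assumed beta distributions, with no loss in the two-point limit. That range is conditional on 36 events, a hazard ratio of 0.99 per point, SD 35 and one-sided 10%, and it concerns PFS in Cohort 1 only. The true figure cannot be derived without the distribution of gpNMB and the share of patients at or above 95%. The primary ORR analysis is unaffected.

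**What to change.** In SAP Section 8.3, state that, if the range of gpNMB expression allows, a Cox model with gpNMB as a continuous covariate will be fitted for PFS, separately by cohort, as the main gpNMB-PFS analysis under the secondary objective. Keep the 95% split in Section 5.3 as a descriptive subgroup display. List any remaining departure from the protocol in Section 12; one example is the ROC analysis for censored data, which the protocol plans and the SAP does not mention. The protocol already specifies the model and the expression data are already to be collected, so the cost is SAP wording.
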